3. INTRODUCTION

3.1. Study Rationale

Systemic Lupus Erythematosus (SLE) is characterized by autoantibodies, including antibodies to double-stranded DNA (dsDNA), and by abnormal B cell activation and differentiation [Davidson, 2001], indicating that therapies which deplete or modulate B cells could be beneficial in treating SLE. Belimumab and rituximab are monoclonal antibodies that achieve their expected pharmacology through different but complementary mechanisms; therefore, based on their mechanisms of action, synergistic effects in the treatment of SLE are possible. Belimumab treatment increases peripheral memory B cells potentially by mobilization from tissues this may include the autoreactive B cell compartment. This study will assess whether co-administration of belimumab and a single cycle of rituximab may optimize treatment with belimumab, resulting in improvements in clinical status with a favorable safety profile, by comparing participants randomized to belimumab plus rituximab vs. belimumab plus rituximab-placebo. An open-label arm is included to provide a qualitative reference to standard therapy.

3.2. Background

Belimumab is an important treatment option for patients with SLE, but significant numbers of patients do not achieve a state of low disease activity, and are still left with moderate level of residual disease activity. There is a large unmet medical need for additional effective treatment which could meaningfully reduce disease-related morbidity and mortality and limit the toxicity associated with traditional treatment regimens such as corticosteroids and immunosuppressants.

Rituximab treatment results in nearly complete depletion of CD20+ B cells in the peripheral blood within hours of treatment. In contrast, relatively high numbers of CD20+ B cells persist in the bone marrow following initial treatment with rituximab [Boumans, 2011]. Belimumab treatment increases peripheral memory B cells potentially by mobilization from tissues this may include the autoreactive B cell compartment from tissues into the periphery. This mobilization would expose these cells to more efficient depletion by rituximab. Continuing belimumab after a single course of rituximab would suppress the B-lymphocyte stimulator (BLyS) elevation observed after rituximab monotherapy, thus suppressing the signal which leads to potential repopulation of autoreactive B cells.

A treatment regimen which could reliably and effectively achieve and maintain low disease activity or remission, including patients with earlier and potentially more reversible disease prior to the development of permanent disability or end-organ damage, would change the paradigm by which SLE is treated today. This patient population has a large unmet medical need as 50% of SLE patients develop end-organ damage within the first 5 years of diagnosis [Urowitz, 2012]. Recent scientific research suggests that a combination treatment with anti-BLyS and anti-CD20 may potentially address this need. Anti-BLyS and anti-CD20 therapeutics operate through different but complementary mechanisms and the addition of a single cycle of rituximab treatment may optimize the effect of belimumab treatment in SLE.

Synergy may emerge through the following mechanisms:

- Belimumab may cause redistribution of memory and germinal center B cells from lymphoid tissue into blood, where they are exposed to higher rituximab concentrations in the absence of local tissue factors that protect the B cells in their niches, which is likely to increase B cell depletion.
- Neutralization of serum BLyS level increases seen after rituximab monotherapy, preventing rapid B cell repopulation which is associated with SLE disease flares.
- Increased stringency of B cell reconstitution in the presence of anti-BLyS therapy with belimumab, resulting in fewer auto-reactive cells being formed after B cell depletion with rituximab.

Preclinical data supporting the hypothesis that a combination of belimumab and rituximab may provide additional efficacy over either agent alone were generated in a human-CD20 expressing mouse model. Experiments using this model demonstrated relative resistance of the marginal zone (MZ) B cell compartment to anti-CD20 antibody monotherapy. Approximately 50% of these cells remained following anti-CD20 mAb as compared to complete depletion of circulating mature B cells. MZ B cells were rendered sensitive to anti-CD20 mAb depletion when they were effectively mobilized from tissues into the vasculature with anti- αL and anti- $\alpha 4$ integrand mAbs. Thus, the tissue B cells were not inherently resistant to anti-CD20 mAb treatment: treatment response was enhanced by prior mobilization of the MZ B cells into the vasculature [Gong, 2005]. Additionally, when mouse BLyS receptor (BR3)-Fc and anti-hCD20 were combined in this model, there was more effective tissue B cell depletion of MZ B cells and follicular (FO) B cells than with either agent alone. Similar observations were made in murine SLE models [Lin, 2015] in which dual targeting resulted in greater efficacy with increased tissue B cell depletion, greater reduction in a range of auto-antibody levels, and significant decreases in total IgG1, IgG2b, IgG3, IgM, and IgA when compared to BLyS inhibition and CD20 B cell depletion alone.

A detailed description of the chemistry, pharmacology, efficacy and safety of belimumab is provided in the most recent version of the Belimumab Investigator's Brochure. Refer to the local rituximab approved product label for description of the chemistry, pharmacology, efficacy, and safety of rituximab.

3.3. Benefit/Risk Assessment

More detailed information about the established benefits and risks of belimumab and rituximab, including expected adverse events (AEs), may be found in the Belimumab Investigator's Brochure and local rituximab approved product label, respectively.

There are no published clinical trial data for the co-administration of belimumab with rituximab; however, the following data were reviewed and no new safety risks beyond what would be expected for either agent alone is suggested from the limited data available from patients who may have had overlapping exposures to belimumab and rituximab:

- The GSK Safety Database of AEs from clinical trials and post-marketing experience
- An insurance claims database (Safety Works)
- In-stream, blinded data from an ongoing GSK study of belimumab in subjects with vasculitis who were induced with high dose corticosteroids and either rituximab or cyclophosphamide
- In stream, blinded data from an ongoing GSK study of belimumab coadministered with rituximab in the treatment of primary Sjögren's syndrome

Given that the experience of co-administration of anti-CD20 and anti-BLyS therapies to date is very limited, robust safety monitoring and stopping rules are being implemented to safeguard subject safety. The key risk assessment and mitigation strategy for this protocol is outlined below and in Section 8.2.

3.3.1. Risk Assessment

Potential Risk of Clinical Significance	Summary of Data/Rationale for Risk	Mitigation Strategy
Investigational Product (IP): Belin	numab (GSK1550188), Rituximab, and Belimumal	b and Rituximab Coadministration
Infections:		
Prolonged B cell suppression and more complete B cell depletion expected; potential for more profound hypogammaglobulinemia with	Rituximab: The rate of serious infections with rituximab in the rheumatoid arthritis (RA) population is 4% per year.	Exclusions based on significant infection history, serologic evidence of past or present HBV or Hepatitis C virus (HCV) infection; IgG
increased risk for serious infections including opportunistic infections (OIs), Progressive multifocal leukoencephalopathy (PML), and Hepatitis B virus (HBV) reactivation.	Reactivation of hepatitis B has also been very rarely reported in RA patients receiving rituximab.	<250 mg/dL (note: <400mg/dL for Germany), IgA deficiency (IgA level <10 mg/dL), neutrophils <1.5X10 ⁹ /L.
Tropulate B virus (TBV) rouservation.	Late onset neutropenia occurs rarely in patients treated with rituximab.	
	Belimumab: The rate of serious infections for SLE is 5% of subjects receiving either belimumab or placebo.	A PML management plan including neurologic questionnaire, patient alert card, and stopping criteria will be utilized. An independent PML
	Belimumab and Rituximab Coadministration: Infections are expected events for both belimumab and rituximab. Cases of PML have been very rarely reported, including fatal events, for both rituximab and belimumab in autoimmune diseases.	Panel is also available for consultations. A diagnosis of PML should be considered in any subject presenting with new-onset or deteriorating neurological signs and symptoms. The subject should be referred to a neurologist or other appropriate specialist for evaluation. If
	There is preclinical evidence for prolonged B cell suppression and more complete B cell depletion as well as effect on IgG1+ plasma cells in the long-lived bone marrow niche thought to be less	PML is confirmed, study agent should be discontinued and consideration should be given to stopping immunosuppressant therapy. If PML is suspected, this should be reported to the Medical Monitor within 24 hrs. The

Potential Risk of Clinical Significance	Summary of Data/Rationale for Risk	Mitigation Strategy	
Investigational Product (IP): Belin	Investigational Product (IP): Belimumab (GSK1550188), Rituximab, and Belimumab and Rituximab Coadministration		
	sensitive to immunotherapy [Lin, 2015] with dual B cell immunotherapy. Assessment of the translatability of the IgG reductions to humans is difficult to make due to species differences in B cell biology and different treatments; however,	appropriateness of continuing study agent, while the case is being assessed, should be discussed.	
	the mouse data raises the hypothetical risk that immunoglobulin levels may reduce more with coadministration treatment.	Monitor patients for signs and symptoms of infection, monitor laboratory values, request that patients report signs of infection. Treat infections immediately and appropriately.	
	Neutropenia:	Neutropenia:	
	SLE disease related neutropenia and Rituximab induced neutropenia may result in further reduction in circulating neutrophils and/or influence timing of this neutropenia onset as compared to when Rituximab is administered alone.	Individual subject's treatment with belimumab and rituximab/rituximab-placebo will be discontinued for (a) life threatening infection; (b) IgG <400 mg/dL if associated with a serious infection.	
		Subjects should be monitored for neutropenia throughout the study. Neutropenia should be managed appropriately according to local practice and clinical judgement should be applied with regard to the appropriateness of continuing study treatment in these subjects.	
		 Study treatment with rituximab/rituximab- placebo (infusions Week 4 and/or Week 6) must be temporarily withheld and the GSK medical monitor consulted about 	

Potential Risk of Clinical Significance	Summary of Data/Rationale for Risk	Mitigation Strategy	
Investigational Product (IP): Belin	Investigational Product (IP): Belimumab (GSK1550188), Rituximab, and Belimumab and Rituximab Coadministration		
		continued dosing if a subject experiences a neutrophil count <1x109/L.	
		 Study treatment with belimumab (Arms A/B and C) must be temporarily withheld and the GSK medical monitor consulted about continued dosing if a subject experiences a neutrophil count <0.5x10⁹/L. 	
Systemic Infusion / Injection-Related Reactions	s, Hypersensitivity Reactions and Immunogenicit	y:	
Serum Sickness: Serum sickness has been associated with rituximab in autoimmune	Rituximab: The incidence of serum sickness associated with rituximab in pSS studies has	Immunogenicity will be evaluated with periodic assessment over the course of the study.	
indications [Meijer, 2010]. There is a potential risk for increased immunogenicity due to cross reactivity which could lead to increased frequency of	ranged from 6-38% [Carubbi, 2014]. Administration of belimumab and rituximab may result in infusion and hypersensitivity reactions, which can be severe and can be fatal. Delay in	A pre-medication regimen will be given before each rituximab/rituximab placebo infusion: methylprednisolone 100 mg IV, an antihistamine and acetaminophen or equivalent.	
hypersensitivity reactions, particularly of the delayed type.	the onset of serious hypersensitivity reactions can occur. Both rituximab and belimumab have been associated with delayed type non-acute Hypersensitivity reaction (HSR)/serum sickness, although no relationship to Anti-drug Antibody (ADA) has been established.	Subjects should remain under clinical supervision for 3 hours after completion of the first belimumab injection and the rituximab/placebo infusions. Should symptoms of acute hypersensitivity occur, an extended period of monitoring may be appropriate, based on	
	Belimumab and Rituximab Coadministration: Incidences of hypersensitivity and infusion reactions have been noted to be higher with co- administration vs. mono-biologic therapy but no	clinical judgement. If subjects are to receive belimumab after 4 consecutive weeks of not receiving belimumab, the first belimumab dose must be administered in the clinic and subject	

Potential Risk of Clinical Significance	Summary of Data/Rationale for Risk	Mitigation Strategy	
Investigational Product (IP): Beli	Investigational Product (IP): Belimumab (GSK1550188), Rituximab, and Belimumab and Rituximab Coadministration		
	association with ADA has been established [Weinblatt, 2006].	should remain under clinical supervision for 3 hours after the completion of the dose.	
		Patients will be given an alert card for HSR and delayed HSR/serum sickness.	
Malignancy:			
There is an increased risk of malignancy, including Non-Hodgkin's lymphoma, in SLE. There is a theoretical increased risk of malignancy with combination immunosuppressive mechanisms.	Belimumab and Rituximab: Immunomodulatory drugs like rituximab and belimumab may increase the risk of malignancy. To date, no causal relationship between belimumab or rituximab and malignancy, including B cell lymphoma, has been detected, both of which have been administered long term and in combination with other immunosuppressants of various mechanisms.	Subjects with a history of malignancy in the 5 yrs prior to randomization, except for adequately treated basal or squamous cell cancers of the skin, or carcinoma in situ of the uterine cervix, will be excluded. Monitor patients for signs and symptoms of malignancy, monitor laboratory values, request that patients report signs and symptoms. Treat appropriately.	
Interaction with Vaccinations:			
There is a risk of reduced antibody titers with mono and dual B cell immunotherapy. The potential synergistic effect of rituximab and	Rituximab: As described in the label [Rituxan package insert, 2016], the response to pneumococcal vaccination (a T cell independent	Immunization with live vaccines is prohibited from 30 days prior to Day 1 and during belimumab use.	
belimumab may result in a prolonged B cell depletion that could have a similar inhibitory impact on vaccine responses as administering repeated doses of rituximab.	antigen) as measured by an increase in antibody titers to at least 6 of 12 serotypes was lower in patients treated with rituximab plus methotrexate (MTX) as compared to patients treated with MTX alone (19% vs. 61%). Additionally, a lower proportion of patients in the rituximab plus MTX	Subjects' vaccination status should be assessed and current immunization guidelines followed; all necessary vaccinations should be administered if possible no later than 30 days prior to Day 1.	

Potential Risk of Clinical Significance	Summary of Data/Rationale for Risk	Mitigation Strategy
Investigational Product (IP): Belin	numab (GSK1550188), Rituximab, and Belimumal	b and Rituximab Coadministration
	group developed detectable levels of anti- keyhole limpet hemocyanin antibodies (a novel protein antigen) after vaccination compared to patients on MTX alone (47% vs. 93%).	
	In a combination study, median antibody titers (tetanus, diphtheria, pneumococcus) at Week 32 were reduced from baseline in atacicept (recombinant fusion protein which inhibits BLyS and APRIL) but not placebo-treated patients who had been previously treated with rituximab. However, these values recovered close to baseline by Week 16 of the follow-up, there were few shifts to below protective titers, and no between group differences with respect to the frequency of shifts.	
	frequency of shifts. Belimumab: The efficacy of concurrent vaccination in patients receiving belimumab is not known; however, in the belimumab vaccination trial, evaluation of the impact of belimumab treatment on response to ontreatment vaccination with 23-valent pneumococcal vaccine revealed that immune responses to the different serotypes were similar in SLE patients receiving belimumab compared with those not receiving treatment at the time of vaccination.	

Potential Risk of Clinical Significance	Summary of Data/Rationale for Risk	Mitigation Strategy
Investigational Product (IP): Belimumab (GSK1550188), Rituximab, and Belimumab and Rituximab Coadministration		
Psychiatric Events:		
There is an identified risk of psychiatric events with belimumab and rituximab.	Rituximab: Depression and anxiety were common AEs in rituximab RA trials.	Subjects who, in the investigator's opinion, pose a significant suicide risk will be excluded.
	Belimumab: There have been reports of depression and suicidality in patients receiving	The Columbia-Suicide Severity Rating Scale (C-SSRS) will be completed at each visit
	belimumab.	Subjects will be monitored closely for signs and symptoms of psychiatric illness including depression and suicidal ideation. Subjects displaying such signs and symptoms will be treated appropriately and referred as necessary to specialty psychiatric care.
Cardiac Disorders:		
	Rituximab: Angina pectoris, cardiac arrhythmias such as atrial flutter and fibrillation, heart failure and/or myocardial infarction have occurred in patients treated with rituximab. There is no data on the safety of rituximab in patients with moderate to severe heart failure or severe, uncontrolled Cardiovascular (CV) disease. Belimumab and Rituximab: Hypotension may accompany infusion/postinjection systemic reactions with both rituximab and belimumab.	Exclude subjects with severe heart failure (New York Heart Association, Class IV) or other severe, uncontrolled cardiac disease. Closely monitor any patients with cardiac history or those who have experienced prior cardiopulmonary adverse reactions during administration of rituximab/rituximab placebo. Consider withholding antihypertensive medications 12 hours prior to rituximab/rituximab placebo infusion.

Potential Risk of Clinical Significance	Summary of Data/Rationale for Risk	Mitigation Strategy	
Investigational Product (IP): Belin	Investigational Product (IP): Belimumab (GSK1550188), Rituximab, and Belimumab and Rituximab Coadministration		
Severe Skin reactions:			
	Rituximab: Severe skin reactions such as Toxic Epidermal Necrolysis and Stevens-Johnson syndrome; some with fatal outcome, have been reported with rituximab.	Permanently discontinue treatment in the case of such an event with suspected relationship to treatment.	
Posterior Reversible Encephalopathy Syndrom	Posterior Reversible Encephalopathy Syndrome (PRES):		
	Rituximab: Cases of Posterior reversible encephalopathy syndrome (PRES) / reversible posterior leukoencephalopathy syndrome (RPLS) have been reported. Signs and symptoms included visual disturbance, headache, seizures and altered mental status, with or without associated hypertension. A diagnosis of PRES/RPLS requires confirmation by brain imaging. The reported cases had recognized risk factors for PRES/RPLS, including the patients' underlying disease, hypertension, immunosuppressive therapy and/or chemotherapy.	Medical monitor will be notified of any new neurologic symptoms. Medical monitor and investigator will consider the possibility of PRES in differential diagnosis.	

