All participants should be monitored closely for infection. Participants who develop IgG <250 mg/dL confirmed by repeat test 1 week (>2 days) after the initial result, will have study treatment withheld, and the investigator must contact the Medical Monitor to determine if study treatment should be continued. In addition, increased vigilance for infection is recommended in participants who develop IgG <550 mg/dL. Those with a decrease in IgG below 400 mg/dL that is associated with a serious infection (i.e., an infection reported as an SAE) will be withdrawn from study treatment. In addition, if any participant develops a life-threatening infection regardless of IgG status, the investigator must contact the Medical Monitor to determine whether study treatment should be continued.

Severe skin reactions such as Toxic Epidermal Necrolysis and Stevens-Johnson syndrome, some with fatal outcome, have been reported with the use of rituximab. In case of such an event, treatment should be permanently discontinued.

A participant will be withdrawn from study treatment if he or she meets liver stopping criteria (defined in Section 8.2.1), presents with suicidal ideation of type 4 or 5 on the C-SSRS, or in the investigator's judgment, the participant is at risk for a suicide attempt. Participants who are withdrawn from study treatment will remain in the study for observation and continue to have all safety and efficacy assessments.

For any study participants exhibiting symptoms consistent with COVID-19, please consider holding dosing of investigational product (IP) and consult with the Medical Monitor. If a participant tests positive for COVID-19, or if no testing is available, hold dosing of IP until symptoms resolve and contact the Medical Monitor. If a positive COVID-19 test result is reported, please consult with the Medical Monitor on whether resolution of symptoms alone, without retesting, is enough to resume dosing of the investigational product.

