- Severe: An event that prevents normal everyday activities. An AE that is assessed as severe should not be confused with an SAE. Severe is a category utilized for rating the intensity of an event; and both AE and SAE can be assessed as severe.

An event is defined as 'serious' when it meets at least 1 of the predefined outcomes as described in the definition of an SAE, NOT when it is rated as severe.

Assessment of Causality

- The investigator is obligated to assess the relationship between study treatment and each occurrence of each AE/SAE.
- A "reasonable possibility" of a relationship conveys that there are facts, evidence, and/or arguments to suggest a causal relationship, rather than a relationship cannot be ruled out.
- The investigator will use clinical judgment to determine the relationship.
- Alternative causes, such as underlying disease(s), concomitant therapy, and other risk factors, as well as the temporal relationship of the event to study treatment administration will be considered and investigated.
- The investigator will also consult the Investigator's Brochure (IB) and/or Product Information, for marketed products, in his/her assessment.
- For each AE/SAE, the investigator must document in the medical notes that he/she has reviewed the AE/SAE and has provided an assessment of causality.
- There may be situations in which an SAE has occurred and the investigator has minimal information to include in the initial report to GSK. However, it is very important that the investigator always make an assessment of causality for every event before the initial transmission of the SAE data to GSK.
- The investigator may change his/her opinion of causality in light of follow-up information and send an SAE follow-up report with the updated causality

assessment.

• The causality assessment is one of the criteria used when determining regulatory reporting requirements.

Follow-up of AE and SAE

- The investigator is obligated to perform or arrange for the conduct of supplemental measurements and/or evaluations as medically indicated or as requested by GSK to elucidate the nature and/or causality of the AE or SAE as fully as possible. This may include additional laboratory tests or investigations, histopathological examinations, or consultation with other health care professionals.

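### Protocol Sections 3.3.1 and 8.2 state different permanent-stop rules for severe skin reactions that are not suspected to be treatment-related

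*Protocol*

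**What the plan says.** Section 3.3 of the protocol explains where its safety rules are found: "The key risk assessment and mitigation strategy for this protocol is outlined below and in Section 8.2". Both of those places address severe skin reactions.

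- **Section 3.3.1, risk table.** The risk is described as "Rituximab: Severe skin reactions such as Toxic Epidermal Necrolysis and Stevens-Johnson syndrome; some with fatal outcome, have been reported with rituximab". The mitigation column reads: "Permanently discontinue treatment in the case of such an event with suspected relationship to treatment".
- **Section 8.2, Discontinuation of Study Treatment.** The risk is described as "Severe skin reactions such as Toxic Epidermal Necrolysis and Stevens-Johnson syndrome, some with fatal outcome, have been reported with the use of rituximab". The instruction that follows is: "In case of such an event, treatment should be permanently discontinued".

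Relatedness is judged at the site. Appendix 7, under Assessment of Causality, says: "The investigator is obligated to assess the relationship between study treatment and each occurrence of each AE/SAE".

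**The concern.** The risk table attaches a causality condition to a permanent-stop instruction. Section 8.2 gives the instruction for the same events without that condition. An investigator who attributes a reaction to a background drug or to another cause would stop treatment permanently under one passage and would not be told to do so under the other.

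Two things are at stake. The first is participant safety: both passages record that some of these reactions were fatal, and Section 3.3 justifies its stopping rules by how little experience exists with giving the two agents together. The second is conduct: if dosing continues after an event judged unrelated, it departs from Section 8.2 but fits the wording of Section 3.3.1. Whether that is a deviation then depends on which passage is read.

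**Working it through.** No arithmetic applies. The check compares the two passages case by case, then looks for anything elsewhere that settles the difference.

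**1. Same events?** Yes. The two descriptions quoted above name the same two conditions, note fatal outcomes, and tie the risk to rituximab in almost identical terms.

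**2. Same rule?**

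| Investigator's judgement | Section 3.3.1 | Section 8.2 |
|---|---|---|
| Relationship suspected | Permanent stop | Permanent stop |
| Relationship not suspected | Permanent stop not triggered | Permanent stop |

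The rules diverge in the second row only.

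**3. Could the condition be implicit in Section 8.2?** Elsewhere in the same section, conditions are written out. The provision for delaying or withholding a dose applies to events the investigator believes may be related to study treatment, and the withdrawal rule for IgG below 400 mg/dL applies when a serious infection accompanies it. The skin-reaction sentence has no comparable condition.

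**4. Does another passage decide?** Section 3.3 points to both places without ranking them. No other rule for severe skin reactions appears in the protocol or the SAP.

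**5. Can the second row arise?** Yes. Appendix 7 asks the investigator to weigh other explanations, including underlying disease and concomitant therapy, and participants enter on background SLE drugs (Section 6.1). Under Section 5.1, rituximab or its placebo is scheduled only at Weeks 4 and 6, while belimumab runs weekly to Week 51 in Arms A and B and to Week 103 in Arm C. Once the infusions are complete, the practical question is whether belimumab continues, and for an event not suspected to be related the two passages answer it differently.

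**6. Does it reach the analysis?** Only at the margin. SAP Section 7.1.1 states that discontinuing investigational product is not a component of the primary endpoint. It does matter for supportive work. In the scenario table of SAP Section 15.6.4, take a participant with a Week 52 score of 2 or less, no treatment failure and no study withdrawal:

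| Estimand | Product continued | Product stopped |
|---|---|---|
| Hybrid (main) | Responder | Responder |
| Composite | Responder | Non-responder |
| Hybrid On Treatment | Responder | Excluded |
| Treatment Policy | Responder | Responder |

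A stop in Year 1 that leads to four or more consecutive missed belimumab doses also falls under the criteria assessed for exclusion from the per-protocol population (SAP Section 15.1.1). So the same clinical event could be classified differently in supportive analyses according to which passage a site followed.

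**The case against.** The strongest reply is that the passages do not strictly contradict each other. The risk table does not say that treatment stops only when a relationship is suspected. It is silent on unrelated events and nowhere permits dosing to continue, so a site that follows Section 8.2 satisfies both. Section 8.2 is also the operational section on stopping, and Section 3.3 sends the reader there. Its instruction follows a sentence about reactions reported with rituximab, so it could be read as meaning treatment-associated reactions, which would remove the difference.

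The divergent case is also narrow. It needs a reaction of this type with no suspected relationship, in a trial where investigators in Arms A and B are blinded to rituximab (Section 7.4). Arm C receives no study rituximab, the drug for which both passages describe the risk.

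Finally, other safeguards apply whichever sentence is read: immediate safety concerns are discussed with the sponsor (Section 9), SAEs are reported within 24 hours (Section 9.7.1), unacceptable toxicity is a separate ground for withdrawal from treatment (Section 8.2), and the monitoring committee is told of life-threatening or fatal SAEs within 72 hours (Section 10.4.4).

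Much of this stands. The word 'only' is absent, following Section 8.2 meets both texts, the case is rare, and no site would be acting alone. It does not remove the difference. A qualifier on a stop instruction is naturally read as limiting it; otherwise it does no work. The restricted reading of Section 8.2 is possible, but it would need to be written down, as it is in the risk table. Blinding does not close the gap either, because Appendix 7 bases a reasonable possibility of relationship on evidence suggesting a causal link, not on an inability to rule one out. The general safeguards bring the event to the sponsor's attention but do not say which rule governs it.

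**Conclusion.** The concern holds. The protocol gives two versions of a safety stop rule for the same events, and they diverge for every event not suspected to be related to treatment. The documents give no rate for these events, so the expected number affected cannot be stated; it should be small. Sample size and power do not depend on the rule, and the primary endpoint does not count stopping study treatment as a component. Effects on the analysis are limited to the classification of a rare participant in supportive estimands or populations.

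This is a minor inconsistency that is worth correcting because of the seriousness of the event. The conclusion rests on reading the risk table's qualifier as a limit on the instruction. It also assumes that the Study Reference Manual and the Protocol Deviation Management Plan, which are not among the documents reviewed, do not already settle the matter. No view is taken on which rule is clinically right.

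**What to change.** Reconcile Section 3.3.1 and Section 8.2 so that both state the same discontinuation rule for severe skin reactions, and in particular so that both say the same thing about an event not suspected to be related. The choice of rule belongs to the sponsor's clinical and safety functions. Any site guidance or deviation plan that repeats the rule should be aligned with the reconciled text. The protocol change is one sentence in the next amendment, and the planned statistical methods need no change.
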